5.0 PATIENTS

5.1 INCLUSION CRITERIA

1. Age \geq 18 years old.
2. Life Expectancy $>$ 12 weeks.
3. Subjects must be willing and able to comply with scheduled visits, treatment requirements of the study.
4. At least one measurable untreated brain lesion \geq 0.5 cm and $<$ 3.0 cm in the longest axis according to modified RECIST
- 1.1. Prior SRS with up to 10 lesions treated with at least a 14 day interval is allowed as long as the previous treatment volume does not overlap with the current targets. The target could be a previously irradiated lesion with clear evidence of progression.
6. Have a performance status of 0 or 1 on the ECOG Performance Scale.
7. Subjects must be free of neurologic signs and symptoms related to metastatic brain lesions and must not have required or received systemic corticosteroid therapy in the 10 days prior to beginning protocol therapy.
8. Prior treatment with immunotherapy and targeted therapy allowed as long as it did not include a combination of MEKi + anti-PD(L)-1 antibody and is $>$ 14 days prior to start of protocol therapy. All tumor types will be eligible and included in the dose escalation phase. Dose expansions will include 10 patients each from lung, breast, and melanoma.
9. Patients with melanoma must have received prior PD-1 based therapy.
10. Patients with NSCLC must have received prior PD-1 based therapy.
11. Patients with TNBC and HR+ are included (any number of prior lines of therapy- including IO naïve patients).
12. For HR+ patients, patients are allowed to receive endocrine therapy (anastrozole, letrozole, exemestane, or fulvestrant). Concurrent CDK4/6 inhibitors will not be allowed.
13. Systematic radiation therapy is allowed ($>$ 14 day washout)
14. Prior platinum-based chemotherapy for NSCLC patients is allowed
15. Adequate organ function as described below:

System	Laboratory Value
Hematological	
Absolute neutrophil count (ANC)	$\geq 1500/\mu\text{L}$
Platelets	$\geq 100\,000/\mu\text{L}$

Hemoglobin	$\geq 9.0 \text{ g/dL}$ or $\geq 5.6 \text{ mmol/L}^a$
Renal	
Creatinine OR	$\leq 1.5 \times \text{ULN}$ OR
Measured or calculated ^b creatinine clearance (GFR can also be used in place of creatinine or CrCl)	$\geq 60 \text{ mL/min}$ for participant with creatinine levels $>1.5 \times$ institutional ULN
Hepatic	
Total bilirubin	$\leq 1.5 \times \text{ULN}$ OR direct bilirubin $\leq \text{ULN}$ for participants with total bilirubin levels $>1.5 \times \text{ULN}$

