6.1.1 DOSAGE AND ADMINISTRATION

The dose for Bintrafusp Alfa (M7824) is a flat dose of 1200mg. Subjects will receive Bintrafusp Alfa (M7824) once every 2 weeks.. Subjects who have experienced a persistent, confirmed PR or CR may continue treatment through the end of 12 months, although additional treatment is possible. If the Principal Investigator believes that a subject may benefit from treatment beyond

12 months, it may be permissible after discussion with the EMD Serono. If there is no evidence of radiographic or clinical progression, then the patient may continue on study at the discretion of the principal investigator.

Participants who are discontinued due to an AE that are subsequently well managed or resolved after stopping therapy, but prior to the end of the study. Prior to reinitiation, the Principal Investigator will need to confirm that the benefit of reinitiating treatment outweighs any risk involved, such as that which led to initial treatment discontinuation. For participants with only stable disease at the time of discontinuation, the Principal Investigator should confirm that no other reasonable treatment options are available.

In addition, to be eligible for reinitiation (after dose delay), the participant must not have previously withdrawn consent for this trial and should have been followed up with regular eCRF documented evaluation scans up to reinitiation of treatment.

Prior to reinitiation of the study intervention, malignant disease must be radiologically restaged within 28 days of dosing to assess all known disease sites. Additionally, relevant safety laboratory assessments, including both full hematology and full chemistry results within 2 weeks, must be available and verified. The Principal Investigator will determine whether additional evaluation and work up are required on a case-by-case basis. A discussion with the study team is warranted to determine whether PK/biomarker testing is indicated upon restarting treatment.

The participant should reinitiate treatment at the treatment phase visit where they left off according to the Schedule of Activities. Participants who reinitiate treatment should stay on study and should be treated and monitored according the Schedule of Activities for the rest of the study.

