In patients who have imaging findings that meet RANO criteria for progressive disease^{16–18} within 6 months of starting immunotherapy including the development of new lesions, confirmation of radiographic progression on follow-up imaging before defining the patient as non- responsive to treatment might be needed provided that the patient does not have new or substantially worse neurological deficits. Such patients might be allowed a window of 3 months before confirming disease progression with the scan that first showed initial progressive changes as the new reference scan for comparison with subsequent imaging studies. If RANO criteria for progressive disease are met on the follow-up scan 3 months later, non-responsiveness to treatment should be assumed, and the date of progressive disease should be back-dated to the initial date when it was first identified (table 1). Patients who develop substantial new or worsened neurological deficits not due to comorbid events or a change in co-administered medication at any time within the 3-month follow-up window should be designated as non-responsive to treatment and should discontinue immunotherapy. For these patients, the date of actual tumor progression should also be back-dated to the date when radiographic progressive disease was initially identified.

RANO and iRANO criteria (Brain Metastases)

	Brain metastases
COMPLETE TARGET	Disappearance of all enhancing target and non-lesions for ≥ 4 weeks; no new lesions; no steroids; clinically stable or improved
PARTIAL RESPONSE	$\geq 30\%$ decrease in sum of longest diameters of target lesions for ≥ 4 weeks; no new lesions; stable or decreased steroid dose; clinically stable or improved
MINOR RESPONSE	NA
STABLE DISEASE	Does not qualify for complete response, partial response, or progressive disease

Proprietary Information of MD Anderson

PROGRESSIVE DISEASE	$\geq 20\%$ increase in the sum of longest diameters of target lesions; or unequivocal progression of enhancing non-target lesions; or new lesions; or substantial clinical decline
----------------------------	---

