The RECIST criteria should be used to assess response to treatment. Only patients with measurable disease should be entered in the study. Measurable extracranial disease is defined as the presence of one lesion that can be accurately measured in at least one dimension (longest diameter to be recorded) as ≥ 2.0 cm with conventional techniques (or as ≥ 1.0 cm by spiral CT). Evaluable lesions should be followed for the assessment of response. Non-measurable lesions include bone lesions, ascites, pleural/pericardial effusion, lymphangitic carcinomatosis, abdominal masses that are not confirmed by CT, and cystic lesions. Disease progression and response evaluations for intracranial and extracranial disease will be determined according to the definitions established in the Response Evaluation Criteria in Solid Tumours (RECIST v1.1). Minor modifications will be applied to the assessment of intracranial lesions:

- General: target lesions should be representative of the subject's baseline tumor burden and should be selected based on their size (i.e. lesions with the longest diameter) and their suitability for accurate repeat assessment.
- Intracranial lesions: (the modifications to RECIST v1.1. impact the number and the minimal size of the target lesions selected at baseline) up to five lesions should be selected as target lesions; all brain lesions in excess of these five target lesions have to be regarded as non-target lesions. Measurable lesions are defined as those that can be accurately measured in at least one dimension with the longest diameter ≥ 5 mm when evaluated with contrast-enhanced MRI. Contrast-enhanced MRI is the only imaging modality accepted for assessment of intracranial lesions.
- Extracranial lesions: up to two lesions per organ representative of all involved organs should be selected as target lesions; the total number of target lesions should not exceed five and all lesions in excess of these five target lesions have to be regarded as non-target lesions.

Baseline Documentation of Intracranial Target and Non-Target Lesions

- All baseline lesion assessments must be performed within 28 days of the first dose of study treatment.

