- Measurable and non-measurable intracranial (i.e. brain parenchyma) lesions up to a maximum of 5 lesions should be identified as target lesions, and recorded and measured at baseline. These lesions should be selected on the basis of their size (lesions with the longest diameter) and their suitability for accurate repeated measurements (either by imaging techniques or clinically).
- Cystic lesions thought to represent cystic metastases should not be selected as target lesions when other suitable target lesions are available.
- Measurable intracranial lesions that have been previously irradiated and have not been shown to be progressing following irradiation should not be considered as target

Proprietary Information of MD Anderson

lesions. All other intracranial lesions should be identified as non-target and should also be recorded at baseline. Measurements of non-target lesions are not required, but the presence or absence of each should be noted throughout follow-up.

Baseline Documentation of Extracranial Target and Non-Target Lesions

- All baseline lesion assessments must be performed within 28 days of the first dose of study treatment.
- Lymph nodes that have a short axis of <10mm are considered non-pathological and should not be recorded or followed.
- Pathological lymph nodes with <15mm and ≥ 10 mm short axis are considered non measurable.
- Pathological lymph nodes with ≥ 15 mm short axis are considered measurable and can be selected as target lesions, however lymph nodes should not be selected as target lesions when other suitable target lesions are available.
- Measurable lesions up to a maximum of 2 lesions per organ and 5 lesions in total, representative of all involved extracranial organs, should be identified as target lesions, and recorded and measured at baseline. These lesions should be selected on the basis of their size (lesions with the longest diameter) and their suitability for accurate repeated measurements (either by imaging techniques or clinically).
- Cystic lesions thought to represent cystic metastases should not be selected as target lesions when other suitable target lesions are available.
- Measurable extracranial lesions that have been previously irradiated and have not been shown to be progressing following irradiation should not be considered as target lesions.
- Lytic bone lesions or mixed lytic-blastic lesions, with identifiable soft tissue components, that can be evaluated by CT or MRI can be considered measurable.

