- Bone scans, FDG-PET scans or X-rays are not considered adequate imaging techniques to measure bone lesions.
- All other lesions (or sites of disease, excluding the brain) should be identified as non-target and should also be recorded at baseline.
- Non-target lesions will be grouped by organ. Measurements of these lesions are not required, but the presence or absence of each should be noted throughout follow-up.

Overall Intracranial Response - Evaluation of Intracranial Target Lesions

Definitions for assessment of response for intracranial target lesion(s) are as follows:

- Complete Response (CR): Disappearance of all target lesions.
- Partial Response (PR): At least a 30% decrease in the sum of the diameters of target lesions, taking as a reference, the baseline sum of the diameters (e.g. percent change from baseline).
- Stable Disease (SD): Neither sufficient shrinkage to qualify for PR nor sufficient increase to qualify for progressive disease.

Proprietary Information of MD Anderson

- Progressive Disease (PD): At least a 20% increase in the sum of the diameters of target lesions, taking as a reference, the smallest sum of diameters recorded since the treatment started (e.g. percent change from nadir, where nadir is defined as the smallest sum of diameters recorded since treatment start). In addition, the sum must have an absolute increase from nadir of 5mm.
- Not Evaluable (NE): Cannot be classified by one of the four preceding definitions.

Note: If an intracranial target lesion disappears and reappears at a subsequent time point it should continue to be measured. The response at the time when the lesion reappears will depend upon the status of the other lesions. For example, if the disease had reached a CR status then PD would be documented at the time of reappearance. However, if the response status was PR or SD, the diameter of the reappearing lesion should be added to the remaining diameters and response determined based on percent change from baseline and percent change from nadir.

- Patients, who in the opinion of the treating physician investigator have had a substantial decline in their performance status and have clinical evidence of progressive disease may be classified as having progressive disease.

Appendix 2: Current National Cancer Institute Common Terminology Criteria for Adverse Events (NCI CTCAE Version 5.0)

Please use the following link to the NCI CTCAE website:

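### Appendix 2 states no confirmation or minimum duration for an intracranial CR or PR under modified RECIST 1.1, so measurement noise can inflate that response rate, mainly in patients whose only target is near 5 mm

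*Combined protocol and SAP*

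**What the plan says.** Section 8.1.4 makes brain MRI read by modified RECIST 1.1 the main method of disease assessment. Section 4.2 lists the intracranial objective response rate by RANO-BM, iRANO and RECIST 1.1 as a secondary objective.

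The relevant rules are these:

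- **Entry.** Section 5.1, item 4 requires "At least one measurable untreated brain lesion", from 0.5 cm to under 3.0 cm.
- **Measurability.** Appendix 2 (RECIST v1.1) counts a brain lesion "with the longest diameter ≥ 5 mm when evaluated with contrast-enhanced MRI", and "up to five lesions should be selected as target lesions".
- **Partial response, modified RECIST.** "At least a 30% decrease in the sum of the diameters of target lesions, taking as a reference, the baseline sum". Complete response is the disappearance of all targets. Neither carries a duration, a confirming scan or a minimum change in millimetres.
- **Progression, modified RECIST.** A 20% rise from nadir, plus an absolute rise of 5 mm.
- **Partial response, Appendix 1 brain-metastasis table (RANO and iRANO).** A 30% "decrease in sum of longest diameters of target lesions for" at least 4 weeks, with no new lesions and with steroid and clinical conditions.

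The word confirmed appears once in connection with response, in Section 6.1.1: "Subjects who have experienced a persistent, confirmed PR or CR may continue treatment through the end of 12 months". That sentence concerns treatment duration and does not define the term. Section 9.3 gives no definition of intracranial response that would supply one.

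**The concern.** Three criteria are applied to the same scans and reported for the same endpoint. Two require the shrinkage to last. The third, which is the trial's main criterion, does not say so. Its text protects progression against small-lesion noise but not response: for a sole 5 mm lesion, progression needs a rise of 5 mm, while response needs a fall of 1.5 mm on any one scan.

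Two features push the same way. Selecting lesions that read at least 5 mm at baseline favours readings that are too high, so later readings tend to fall back. Repeated scans also give repeated chances to cross the line. Reading is local (Section 8.8) and the trial is open-label.

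At stake is upward bias in a response rate that has no control arm to reveal it. The goal is 10 patients per tumour type, so one false responder moves a cohort's rate by 10 percentage points. Section 9.2 says the phase II data are meant to inform later, larger studies.

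**Working it through.** The plan gives no target, null rate or measurement error for intracranial response, so there is no stated figure to reproduce.

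**Inputs from the documents.** Measurable size is 5 mm, PR is a 30% fall in the sum, and there are 1 to 5 targets. The footnote to Table 3 schedules MRI every 4 weeks to week 16 and then every 8. That gives weeks 4, 8, 12, 16 and 24, which is five scans by week 24, and eight by week 52. Section 8.1.4 moves to 8-weekly scans after week 12. It reaches five scans by week 28 and also eight by week 52.

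**Assumptions not in the documents.** Reading error is normal and independent, with SD *s* of 0.25 to 1.0 mm per lesion. True size is constant, all scans are done, and every baseline reading is at least 5 mm.

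**Fall needed for PR.**

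- Sole 5 mm lesion: 0.30 × 5 = 1.5 mm
- Sole 10 mm lesion: 0.30 × 10 = 3.0 mm
- Five 5 mm lesions: 0.30 × 25 = 7.5 mm

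**One scan, no true change.** With true sum *D* over *m* lesions, a false PR needs follow-up reading ≤ 0.7 × baseline reading. Before the entry cut-off is applied, the probability is Φ(−0.3*D* / (*s*√(1.49*m*))). For *D* = 5 and *m* = 1:

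- *s* = 0.25: practically 0
- *s* = 0.5: Φ(−1.5/0.610) = Φ(−2.46) = 0.7%
- *s* = 0.75: Φ(−1.5/0.916) = Φ(−1.64) = 5.1%
- *s* = 1.0: Φ(−1.5/1.221) = Φ(−1.23) = 11%

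Requiring the baseline reading to be at least 5 mm keeps only the high half of readings of a true 5 mm lesion. This roughly doubles the rates, to about 1.4%, 9% and 19% at SD 0.5, 0.75 and 1.0 mm.

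**Any of five scans (unconfirmed) against two consecutive scans (confirmed), by simulation.**

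| Targets | Rule | SD 0.25 | SD 0.5 | SD 0.75 | SD 1.0 |
|---|---|---|---|---|---|
| Sole 5 mm | unconfirmed | 0% | 6% | 34% | 59% |
| | confirmed | 0% | 0.3% | 5% | 15% |
| Sole, uniform 5–10 mm | unconfirmed | 0% | 0.5% | 5.6% | 16% |
| | confirmed | 0% | 0.01% | 0.5% | 2.3% |
| Sole, uniform 5–30 mm | unconfirmed | 0% | 0.1% | 1% | 3% |
| | confirmed | 0% | 0% | 0.1% | 0.4% |

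Over eight scans the sole 5 mm figures at SD 0.5, 0.75 and 1.0 mm become 9%, 46% and 73% unconfirmed, against 0.4%, 7.8% and 22% confirmed. For a sole 15 mm lesion the eight-scan unconfirmed rate is at most 0.1% up to SD 1.0 mm.

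**What this means for a cohort.** If all 10 patients had one lesion drawn evenly from 5–30 mm, the expected number of false responders over five scans is 10 × 0.001 = 0.01 at SD 0.5 mm, 10 × 0.01 = 0.1 at 0.75 mm and 10 × 0.03 = 0.3 at 1.0 mm.

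**The case against.** A reader might infer that measurement noise by itself produces intracranial responders in this trial. The documents do not support that. They give no reading error, and at SD 0.25 mm the false rate is zero under either rule. The large percentages need a sole target close to 5 mm and an error of about 0.75 mm or more. Targets are chosen for size and for suitability for repeat measurement, the qualifying lesion may be almost 3 cm, and up to five are summed. The number of patients expected to have one lesion near 5 mm is not stated.

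The constant-size null is also generous to the concern. If lesions grew by 5% from each scan to the next (an assumption), the sole 5 mm rates at SD 0.5, 0.75 and 1.0 mm would drop from 6/34/59% to about 0.5/9/27%.

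A reader might also infer that the protocol definitely lets one scan count. Appendix 2 says that responses follow RECIST v1.1 and that its changes affect only the number and minimum size of targets. Whether that source adds confirmation cannot be settled from these documents. What can be said is that Appendix 2 then writes out its own CR and PR definitions and puts no confirmation in them.

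Finally, the RANO-BM and iRANO response rates already carry the 4-week condition, and intracranial response is secondary with no decision rule attached.

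All of this stands and limits the size and consequence of the point. It does not remove the gap: as written, two analysts could report different modified-RECIST response rates from the same scans.

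**Conclusion.** The concern holds in a limited form. As written, modified RECIST 1.1 counts an intracranial CR or PR on a single scan, with no duration or absolute floor. That is looser than the Appendix 1 table and out of step with the plan's own progression rule. Noise can therefore bias the RECIST-based intracranial response rate upward.

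The bias is concentrated in patients whose whole target sum is one lesion near 5 mm. There it ranges from nothing to more than half of such patients across the assumed reading errors. Averaged over sole lesions of 5–30 mm it is about 3% or less, and it is near zero for large sums. Wherever the unconfirmed rate is material, confirmation cuts it at least about threefold. These figures rest on the assumed error, constant true size and complete scanning.

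Time to intracranial progression, overall survival, the toxicity stopping rules and dose selection are unaffected. The change is worth making because it is cheap and the rate has no comparator.

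**What to change.** In Appendix 2, require intracranial CR and PR to be confirmed on a scan at least 4 weeks later, matching Appendix 1. Report the modified-RECIST intracranial response rate as confirmed responses, with unconfirmed ones listed separately. This concerns how the endpoint is counted and proposes no change to treatment rules.

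Two small points belong in the same edit:

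- Each scan has a ±7-day window, so two consecutive 4-weekly scans can be as little as 28 − 14 = 14 days apart. State whether the nominal visit satisfies the 4 weeks or whether the next later scan is used.
- Reconcile the 5 mm threshold for measurability with the baseline instruction that reads "Measurable and non-measurable intracranial (i.e. brain parenchyma) lesions up to a maximum of 5 lesions should be identified as target lesions". Targets below the threshold would make the problem worse.

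The cost is a line or two of text. The scheduled MRIs supply the confirming scan while imaging continues. The downside is that a true response first seen on a patient's last scan is not counted as confirmed, so the headline rate will be slightly lower. The separate listing keeps such cases visible.

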4.2 SECONDARY OBJECTIVES

- Intracranial progression 4, 8, 12, 16 weeks and every 8 weeks thereafter.
- Intracranial objective response rate as measured by RANO-BM, iRANO, and RECIST 1.1.
- Time to second intracranial progression after Salvage SRS
- Overall survival rate at 24, 52 and 68 weeks.
- Frequency of grade 3+ intracranial toxicities at 4, 12, 24, 36, 52, and 68 weeks. Frequency of extracranial progression and response rate at 8, 16, 24, every 8 weeks.
- Frequency of neurocognitive decline 12, 24, 36 weeks (optional). Changes in neurocognitive function and health-related quality of life.
- Dose, duration and frequency of steroid use for symptomatic management.
- Evaluation of safety and tolerability of pimasertib/bintrafusp alfa combination

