8.1.4 RESPONSE ASSESSMENT

MRI of the brain will be the primary radiological method of disease assessment using modified RECIST 1.1. Treatment decisions will be made according to modified RECIST 1.1 while other measurement criteria will be utilized as secondary endpoints including iRANO criteria (See Appendix 1). Quantitative imaging changes on multiparametric MRI will be captured to determine early biomarkers of immune response. Standard of care brain MRI with intravenous gadolinium contrast and contrast enhanced CT chest/abdomen/pelvis or PET-CT, as clinically indicated, will be used to assess both intracranial and extracranial disease at Screening and every 4 weeks for the first 12 weeks, then every 8 weeks for the first year, then every 12 weeks until progression or discontinuation of study treatment, whichever comes

later. Imaging window is \pm 7 days. If scans performed within 4 weeks of discontinuation, repeat scans are not required. Screening MRI and CT assessments must occur within 28 days prior to day 1.

If an MRI, CT chest/abdomen/pelvis or PET-CT is not already performed as standard of care per Schedule of Assessments in Section 8.0, the principal investigator may choose to perform either or both procedures for assessing the progress of the patient.

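### Appendix 2's reference for intracranial progression, taken literally, leaves out the baseline sum, so target-lesion growth could not count as progression at week 4 and some progression dates could slip

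*Combined protocol and SAP*

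**What the plan says.** The target-lesion rule is in Appendix 2 (RECIST v1.1 criteria), under the evaluation of intracranial target lesions. Progressive disease needs "At least a 20% increase in the sum of the diameters of target lesions" over the reference, and "In addition, the sum must have an absolute increase from nadir of 5mm". The bullet describes the reference twice, both times as the smallest sum since treatment began. The second description is worded as a definition: "where nadir is defined as the smallest sum of diameters recorded since treatment start". Baseline is not named in either.

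The baseline scan comes before treatment. Appendix 2 says "All baseline lesion assessments must be performed within 28 days of the first dose of study treatment", and section 8.1.4 fixes the direction: "Screening MRI and CT assessments must occur within 28 days prior to day 1".

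Three other places bear on the intended meaning:

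- Appendix 2 opens by adopting RECIST v1.1: "Disease progression and response evaluations for intracranial and extracranial disease will be determined according to the definitions established in the Response Evaluation Criteria". For brain lesions it limits its own changes: "the modifications to RECIST v1.1. impact the number and the minimal size of the target lesions selected at baseline".
- Section 4.2 lists as a secondary objective "Intracranial progression 4, 8, 12, 16 weeks and every 8 weeks thereafter".
- Section 3.0 says an early imaging time point was included so that radiosurgery can be applied to brain lesions that are progressing or not responding.

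Section 9.3.2 determines time to intracranial progression, a phase II primary endpoint, by modified RECIST 1.1. Section 8.1.4 ties treatment decisions to the same criteria.

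**The concern.** An assessor or programmer who applies the printed definition will search the on-treatment sums for the minimum. At the first on-treatment MRI, the only candidate is that scan's own sum. Its change from nadir is zero, so the target-lesion rule can never be met at that visit. From week 8, a patient who grew from the start is compared with an already enlarged sum.

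Growth of existing lesions is a named component of the primary endpoint, and the week-4 scan is the first chance to see it. Two people could date the same patient's progression differently, one taking baseline as the first reference and the other following the text. With 30 patients at the recommended dose, and a goal of 10 per tumour type (section 9.2), a few shifted dates could move a cohort's estimate.

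**Working it through.** The documents state no figure that depends on this definition, so there is none to reproduce. The check applies the rule under two readings.

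**Inputs.** The thresholds are 20% and 5 mm (Appendix 2). Scans are at weeks 4, 8, 12, 16 and every 8 weeks after that (Table 3, footnote f). Section 8.1.4 gives a different schedule after week 12, but both agree on weeks 4, 8 and 12. The lesion sums are assumptions.

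**Rule.** With S the current sum and n the reference, progression requires S ≥ 1.2 × n and S − n ≥ 5 mm. As printed, n is the minimum of the earlier on-treatment sums. In the alternative, n is the minimum of baseline and the earlier on-treatment sums.

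**Direction.** Adding baseline to the set can only lower n or leave it unchanged, and a lower n makes both conditions easier to meet. Progression as printed is therefore never earlier than progression with baseline included.

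**Who is affected.** If the week-4 sum is at or below baseline, including baseline does not change n at any later scan, and there is no growth to detect at week 4. The readings then agree. They can differ only when the week-4 sum is above baseline.

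**Illustrations** (sums in mm at weeks 0, 4, 8, 12):

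| Assumed sums | Baseline included | As printed |
|---|---|---|
| 20, 26, 33.8 | week 4: 26/20 = +30%, +6 mm | week 8: 33.8/26 = +30%, +7.8 mm |
| 40, 46, 52.9, 60.8 | week 8: 52.9/40 = +32%, +12.9 mm | week 12: 60.8/46 = +32%, +14.8 mm (week 8 is only 52.9/46 = +15%) |
| 20, 26, 30, 34 | week 4: +30%, +6 mm | week 12: 34/26 = +31%, +8 mm (week 8 is only +15%, +4 mm) |
| 20, 30, 31, 33 | week 4: +50%, +10 mm | none through week 12: 33/30 = +10%, +3 mm |
| 20, 26, then 26 throughout | week 4: +30%, +6 mm | none through week 48 |
| 20, 15, 15, 21 | week 12: 21/15 = +40%, +6 mm | week 12: the same |

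**Range under steady growth.** Baseline sums of 5, 10, 20, 30, 50 and 100 mm were crossed with growth of 5, 10, 20, 30 and 50% per 4 weeks, giving 6 × 5 = 30 combinations. In 24 the date moves by one scan: 4 weeks early on, or 8 weeks where the move is from week 16 to week 24. In 6 nothing changes, including one (5 mm at 5%) with no progression by week 48 under either reading. These counts describe the grid and do not estimate how often patients would be affected.

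**The case against.** The strongest reply is that nobody would read the sentence this way. Appendix 2 adopts the RECIST v1.1 definitions and says its changes for brain lesions concern only how many target lesions are chosen and how small they may be. The progression reference is not listed as changed. A rule that makes the week-4 scan its own comparator has no content at that visit, yet the plan reports progression at week 4 and schedules the early scan partly to find it. The note on reappearing lesions, just below the progression bullet, uses change from baseline alongside change from nadir, so baseline remains in use after the response bullets.

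Much of this stands. It is good evidence that the literal meaning was not intended. It does not override the definition: Appendix 2 prints its own explicit reference, and no sentence says which text prevails. The note also cuts both ways, since it treats baseline and nadir as separate quantities.

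A reader might go further and infer that no progression can be recorded at week 4. The documents do not support that. New lesions are part of the primary endpoint (Trial Summary), and Appendix 2 lets the investigator classify progression on clinical grounds, though that route is discretionary and requires a substantial decline in performance status. Nor do the documents show that early failures would go unmanaged: section 3.0 covers lesions that are merely not responding, and section 8.10 permits treatment past progression under stated conditions.

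**Conclusion.** The printed reference conflicts with the plan's own statements and should be corrected. Applied as written, it rules out target-lesion progression at week 4. It can also date progression one or two scans late, or miss it, in patients whose target sum is above baseline by week 4 and who have no new-lesion, non-target or clinical progression. In the assumed paths where progression is eventually called, the delay is 0 to 8 weeks. Any error goes one way, towards later progression.

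It would be tempting to conclude that the primary endpoint is in fact biased upward. That does not follow. It requires assessors to apply the literal wording, and enough patients to follow the affected pattern. The documents give no growth or event-rate data, so the effect on the endpoint cannot be computed. Phase II is also an estimation exercise meant to inform larger studies: no efficacy test or efficacy stopping rule depends on the date, and the stopping rules in section 9.2 use toxicity only. The point is a faulty definition that is cheap to correct, not a demonstrated bias.

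This conclusion rests only on the protocol's text. What the RECIST v1.1 publication says about the reference was not used.

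**What to change.** In the progressive-disease bullet of Appendix 2, replace both descriptions of the reference with: the smallest sum of diameters recorded on study, including the baseline sum. Derive all intracranial progression dates, and intracranial progression status at week 4, from that definition.

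The cost is one clause. It needs no extra scans or measurements. Reported time to intracranial progression may be slightly shorter than under the literal wording.
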